In addition, we will update the patient's care provider on a regular basis about medication gaps and other medication issues of their patients. The frequency and mode of contact will be based on their indicated preference, which we will solicit at the start of the study during our clinic presentation. If the provider did not indicate a preference, we will send this information via email on a weekly basis.

Quantitative Analysis

The study will be a randomized controlled study with four treatment arms. When patients are identified through pharmacy refill data to have a 7-day gap in any prescribed CV medication refills, they will be randomized to one of four arms, described in Intervention below. Randomization will be stratified within each of the eight clinics, and within strata defined by number of other CV medication classes that are prescribed at randomization (1-4), using blocks of 4 patients to ensure balance within clinics over time. Thus, within each clinic and number of other medication stratum, each set of 4 consecutively enrolled subjects will be randomized to the four study arms. Treatments will be initiated immediately upon randomization, in response to the 7-day gap.

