- i) Medication-specific PDC: For a given medication class, the model will include fixed effect terms for treatment arm, clinic, patient covariates, and number of other CV medications the patient is prescribed, and a random subject effect for a subject's tendency to have higher or lower PDC compared with other subjects. Covariates to be adjusted for will be selected a priori based on clinical considerations and covariate data quality, the latter assessed after we have enough pilot and baseline data to make the assessment but before examining outcome data.
- 416 All covariates included in outcome models will also be included in imputation models (see

417 below). The analysis will be carried out using daily data to account for the differing numbers of 418 at-risk days across patients, and the possibility that the number of other prescribed CV 419 medications may change during the one year PDC modeling period. The parameter being 420 modeled is the probability that a given day is covered, conditional on fixed and random effects. 421 This approach will account for complications a) varying numbers of at-risk days for different 422 patients and different medication classes, b) defining PDC when considering multiple 423 medication classes, c) adjusting for number of other CV medications prescribed, and d) the non-424 normal bounded distribution of PDC. Due to non-independence of days for a given subject, the 425 binomial assumption will not hold and inference will need to be carried out using bootstrap or 426 Markov chain Monte Carlo (MCMC) methods as described below.

427 428

429

ii) All-medication PDC: Each day for each subject will be coded as whether they have all prescribed and at-risk medications available or not. The same modeling process described above for medication-specific PDC will be used.

430 431 432

433

iii) Average PDC: Medication-specific PDC models will be estimated as described above, and will be used to calculate estimates of average PDC using the standardization methods described below.

434 435 436

437

438

439

440

441

442

443

444

445

446

447

448

449

450

451

452

453

454

Treatment comparisons

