Health system costs: This analysis will examine intervention costs and incremental medical costs associated with the intervention. Cost data will be analyzed using the same methods described above with factors for study arm and health care system/clinic strata, using generalized Gamma regression, which include as special cases lognormal, Gamma and Weibull. The primary dependent variable will be healthcare cost, in total and separated into inpatient, outpatient, and pharmacy cost buckets. The primary independent variable will be the intervention arm the patient was randomized to. Results will be stratified by healthcare system.

Power Assessment

We first estimated sample size required to achieve 80% power for the desired change in the primary outcome, then used current data to show we will be able to achieve this sample size.

Power and sample size: Required sample size was estimated for the primary outcome PDC during the 12 months following randomization. Preliminary data from the VA were used for these estimates. We made the following assumptions: a) Significance using two-sided level 0.05 tests, b) Power at least 80%; c) Difference between treatments in PDC of 10 percentage points; d) Bonferroni adjustment for the 6 pairwise comparisons among the 4 study arms, resulting in adjusted level 0.05/6; e) Analysis stratified by health care system; and f) Within-system and within-treatment residual standard deviation of 12 month PDC equal to 0.247 (mean 0.771), obtained by analysis of 594,466 veterans during the period 01/01/2010 – 09/30/2012 who were prescribed CVD medications. The large SD is due to a highly left-skewed PDC distribution. (We base sample size estimation on t-tests rather than the proposed binomial models since we do not have estimates of quantities needed to carry out power simulations. We may be able to obtain data for the PDC outcome for a set of baseline patients, in which case we will consider a refined power analysis.) Using these assumptions and estimates, and comparing any two treatments using a linear model with the above residual standard deviation of PDC, we estimate using sample size functions in R that we will need N=154 subjects per treatment arm, total

across the three health care systems, for a total of 616 subjects to be randomized across the three health care systems.

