Study description: This individually randomized three-center trial will compare three behavioral nudges based on text and chatbot messaging with usual care to improve adherence to cardiovascular medications.

Setting: The study will be conducted in 17 primary care clinics within 3 health care systems (University of Colorado Health, VA Eastern Colorado Health Care System, and Denver Health Medical Center).

Design: The study will be an individually randomized controlled study with four treatment arms (details of interventions below). Patients become eligible for the study when identified through pharmacy refill data to have a 7-day gap in any prescribed CV medication refills. Eligible patients will be randomized to one of four arms. Randomization will be stratified within each of the clinics, and further stratified within clinics by patients with 1-2 vs 3 or more active CV medication classes at baseline, and using blocks of 4 patients to ensure balance within clinics over time. Thus, within each clinic and number of other medication stratum, each set of 4 consecutively enrolled subjects will be randomized to the four study arms. Treatments will be initiated immediately upon randomization, in response to the 7-day gap.

Intervention: The four treatment arms will be 1) usual care (control); 2) generic text message reminder; 3) text message behavioral nudges only; or 4) text message behavioral nudge plus a pre-programmed AI interactive chat bot designed to identify and resolve barriers to medication refill and adherence.

Delivery of treatments will be as follows:

For patients randomized to one of the three active intervention arms:

- If a patient gaps on a medication at baseline, they receive a text to refill that medication.
 - If a patient gaps on multiple medications at baseline, they receive only one text about all of the medications they gapped on.

- If a patient later gaps on any study medication, they will receive a reminder, regardless of whether they had gapped on or been prescribed the medication at baseline.
- If a patient is removed from a medication, no further texts are sent for that medication. Patients randomized to the control arm receive no texts or other reminders.

2. Study outcomes

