Composite PDC with differing lengths of follow-up: In general, PDC is the sum of observation days covered divided by the sum of observation days. Due to variations from the planned 365 days of assessment, there are several ways of calculating composite PDC for multiple medications. Information on hospitalizations, and on medication changes and cancellations, will be available from the patient's electronic health record. Note that at-risk days is medication specific, as medications may change during the one-year assessment period. Our primary PDC calculation will be PDC-C1 = (sum of numerators of medication-specific PDCs) / (sum of denominators of medication-specific PDCs). This can also be viewed as a weighted sum of medication-specific PDCs with weights equal to the proportion of the 365 target days for which PDC was observed, and equally weights each day on each medication. PDC-C1 will be the outcome definition in the longitudinal models described in section 3.1.a. As a sensitivity

analysis we will also consider an alternate definition, PDC-C2 = average of medication-specific PDCs, which equally weights medications regardless of their length of observation. When all medications are observed for 365 days these definitions are equal. For the longitudinal analyses planned, these definitions will be applied within each longitudinal interval. We will carry out the recommended sensitivity analyses based on pattern mixture models, by assuming various values for difference in means between observed and unobserved data and assessing differences in model conclusions.

3.1.c Adjustment/propensity covariates

The linear weighted GEE model for PDC and the logistic model for propensity of observation will each contain terms for randomization stratification variables health care system (VA, Denver Health or CUHealth), number of CV medications prescribed at baseline (1-2 or 3+), calendar month of randomization; treatment arm, follow-up month from randomization in longitudinal analysis, and treatment by follow-up month interaction; patient demographics age, race, ethnicity, insurance status, and marital status; and comorbidity variables hypertension, hyperlipidemia, coronary artery disease, diabetes, atrial fibrillation, chronic heart failure, chronic kidney disease, cerebrovascular disease, prior myocardial infarction, prior revascularization, depression, PTSD, and substance abuse.

3.1.d Alternate measures of medication adherence

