of particular interest. HTE analyses will be carried out using interactions as recommended in Kent et al., 2010 ²³ and will be considered exploratory.

3.1.f Original power analysis

We first estimate sample size required to achieve 80% power for the desired change in the primary outcome, then used current data to show we will be able to achieve this sample size.

Power and sample size: Required sample size was estimated for the primary outcome PDC during the 12 months following randomization. Preliminary data from the VA were used for these estimates. We made the following assumptions: a) Significance using two-sided level 0.05 tests, b) Power at least 80%; c) Difference between treatments in PDC of 10 percentage points; d) Bonferroni adjustment for the 6 pairwise comparisons among the 4 study arms, resulting in adjusted level 0.05/6 (a conservative alternative of the sequential gatekeeper approach to be used in the final analysis as described above, to simplify the calculation of power); e) Analysis stratified by health care system; and f) Within-system and within-treatment residual standard deviation of 12 month PDC equal to 0.22 (mean 0.732), obtained by analysis of 2,859 veterans during the period 01/01/2017 – 12/31/2017 who were prescribed the medications of interest in this study. The large SD is due to a highly left-skewed PDC distribution. (We base sample size estimation on t-tests rather than the proposed binomial models since we do not have estimates of quantities needed to carry out power simulations. We may be able to obtain data for the PDC outcome for a set of baseline patients, in which case we will consider a refined power analysis.) Using these assumptions and estimates, and comparing any two treatments using a linear model with the above residual standard deviation of PDC, we estimate using sample size functions in R that we will need N=119 subjects per treatment arm, total across the three health care systems, for a total of 476 subjects to be randomized across the three health care systems.

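### SAP 3.1.c adjusts for health care system and has no clinic term, although patients were randomised within clinics: a minor mismatch that is cheap to correct

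*Combined protocol and SAP*

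**What the plan says.** SAP section 3.1.c sets one covariate list for both the weighted GEE model for PDC and the logistic model for being observed. It opens with the "randomization stratification variables health care system (VA, Denver Health or CUHealth), number of CV medications prescribed at baseline (1-2 or 3" or more), and continues with "calendar month of randomization; treatment arm, follow-up month from randomization in longitudinal analysis". Demographics and comorbidities follow. Clinic does not appear.

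The Design paragraph in SAP section 1 describes a different scheme: "Randomization will be stratified within each of the clinics, and further stratified within clinics", the second factor being 1-2 versus 3 or more active CV medication classes, in blocks of 4. It names neither system nor calendar month as a factor. SAP section 3.1.f counts 17 clinics: 4 at the VA, 5 at UCHealth and 8 at Denver Health.

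The protocol, under Quantitative Analysis, also randomised by clinic: "Randomization will be stratified within each of the eight clinics". Under Modeling PDC, for medication-specific PDC, "the model will include fixed effect terms for treatment arm, clinic, patient covariates" and further terms. The SAP's Summary of revision declares that adjustment covariates are now specified in detail, but does not say why clinic was dropped.

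Both power sections work at system level. The protocol's reads "Analysis stratified by health care system; and f) Within-system and within-treatment residual standard deviation of 12 month PDC equal to 0.247"; SAP 3.1.f reads "Analysis stratified by health care system; and f) Within-system and within-treatment residual standard deviation of 12 month PDC equal to 0.22".

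**The concern.** When allocation is balanced within clinics, differences between clinics largely cancel out of the treatment contrast. A model without clinic leaves that variation in the residual, so the standard error counts variance that the design has already removed. Tests become conservative and intervals too wide. The usual remedy is to adjust for the factors used in the randomisation, and 3.1.c appears to intend this but names a coarser factor.

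Two further points arise. The placing of calendar month directly after the two named factors leaves it unclear whether it is meant as a stratification factor. The same list also drives the inverse-probability weights: if early termination of PDC observation differs between clinics of one system, a weight model without clinic would miss that. The documents give nothing from which to size this second effect.

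**Working it through.** **Inputs from the documents**
- Enrolment (SAP, Achieved sample sizes): 1,235 + 7,266 + 1,000 = 9,501, allocated equally, so n = 9,501/4 ≈ 2,375 per arm.
- SD of 12-month PDC: 0.22 (SAP 3.1.f), with 0.247 (protocol, Power Assessment) as an alternative. Both come from VA patients.
- Stage 1 level (SAP 3.1.a): 0.05/3 = 0.0167, taken as two-sided; z = 2.394. For 80% power, z = 0.842.
- Planned effect (SAP 3.1.f): "Difference between treatments in PDC of 10 percentage points".

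**Assumed:** the share s of PDC variance lying between clinics within a system. The range 1-5% is used. The 2-point difference below is only an illustration, chosen near the detectable difference.

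**The plan's own figure.** A two-sample t-test with SD 0.22, difference 0.10, level 0.05/6 and 80% power gives 118.97, so 119 per arm, as SAP 3.1.f states. Nothing here disputes it.

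**Standard errors**
- Reported without clinic: 0.22 × √(2/2,375) = 0.00638.
- True, given balance within clinics: 0.00638 × √(1 − s) = 0.00635 (s = 1%) or 0.00622 (s = 5%).
- Ratio: 1/√(1 − s) = 1.005 or 1.026.

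**Consequences**
- True level without clinic: 2 × [1 − Φ(2.394/√(1 − s))].
- Detectable difference without clinic: 2.394 × reported SE + 0.842 × true SE.
- Detectable difference with clinic: (2.394 + 0.842) × true SE.
- Width of the 98.33% interval: 2 × 2.394 × the SE used.

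| Quantity | s = 1% | s = 5% |
|---|---|---|
| Reported SE too large by | 0.5% | 2.6% |
| True level of the nominal 0.0167 test | 0.0161 | 0.0140 |
| Detectable difference, points: without → with clinic | 2.063 → 2.055 | 2.052 → 2.013 |
| Power at 2 points: without → with clinic | 77.1% → 77.5% | 77.6% → 79.4% |
| 98.33% interval width, points: without → with clinic | 3.06 → 3.04 | 3.06 → 2.98 |
| Detectable difference with SD 0.247, points | 2.316 → 2.307 | 2.304 → 2.260 |

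Power at 10 points is about 100% in every case.

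**Simulation check.** 9,501 patients in 17 clinics by two medication strata, permuted blocks of 4, one pairwise comparison with robust standard errors, 10,000 replicates per value of s:
- At s = 5%, the model with system alone had a mean reported SE of 0.00636 against an empirical SE of 0.00620, and rejected 0.0137 of the time. With clinic, the figures were 0.00621, 0.00620 and 0.0162.
- At s = 2%, rejection was 0.0166 without clinic and 0.0184 with it. The Monte Carlo standard error is about 0.0013, so neither is clearly off nominal.
- The empirical SE was the same with and without clinic at every s tried (0 to 10%).

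**Cost in parameters.** (17 − 1) − (3 − 1) = 14 extra per model. Average clinic size is 1,235/4 ≈ 309 at the VA, 1,000/5 = 200 at UCHealth and 7,266/8 ≈ 908 at Denver Health. Enrolment by individual clinic is not given.

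Both the formulas and the simulation use one complete 12-month value per patient. The weighted monthly GEE and its observation weights were not modelled.

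**The case against.** The strongest objection is that almost nothing is at stake. The gain is a few hundredths of a percentage point at most against a planned 10-point difference. Because the empirical SE is the same either way, the estimate itself becomes no more precise; only the reported error is corrected. That is right, and it is why the point is minor.

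The size also rests on assumptions. The clinic share is not in the documents. What counts is the share left after the other 3.1.c covariates, so 5% may be high. The SDs come from VA patients, who make up 1,235/9,501 = 13% of those enrolled. These limits stand: the third decimals show direction, not precision.

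There is a case for system as well. Clinics are nested in systems, so the label is coarse rather than false. Both power sections assume analysis by system, and SAP 3.1.a describes two disruptions specific to health care systems, which makes system a natural term in the observation model. Clinic effects contain the system main effect, however, so replacing system with clinic loses none of this. The protocol's clinic term belonged to a model since replaced, so dropping it is not in itself an error; what is missing is the reason. The protocol's descriptive balance check by clinic does not put clinic in the model.

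Blocks intended to keep balance over time make it understandable that calendar month sits beside the design factors, but they do not make it one. Finally, the change costs slightly more than wording: it alters the primary model, so it needs a dated SAP revision before unblinding.

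**Conclusion.** The mismatch holds: the SAP randomises by clinic and adjusts by system, without explanation. It is minor. With complete data it causes neither bias in the randomised contrast nor excess type I error. For an assumed clinic share of 1-5%, it makes tests and intervals slightly conservative, and the conclusion about a 10-point difference is unaffected. Any effect through the observation weights cannot be assessed from the documents. The correction is worth making because it uses data already held and makes the primary model match the groups within which patients were randomised, not because the result is at risk.

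**What to change.** In SAP 3.1.c:

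1. Replace the system term with clinic fixed effects (17 levels, nested in system) in both the GEE and the observation model. Keep the 1-2 versus 3+ medication stratum. The treatment-by-system analysis in 3.1.e can stay, because the clinic effects contain the system main effect.
2. Correct the stratification label to clinic and medication-count stratum. State whether calendar month of randomisation belongs under that label or is an ordinary covariate.
3. If small clinics are to be pooled within their system, fix a size threshold before unblinding, for example fewer than 40 patients (ten blocks of 4), rather than deciding by whether a model converges.
4. If system is kept on purpose, state the reason and still correct the label.

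The cost is a dated SAP revision before unblinding and 14 more parameters in each model. No new data are needed, since clinic had to be known to randomise each patient.

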- All materials will be available and sent to patients in both English and Spanish for UCHealth
- and Denver Health patients. If they have previously specified in their contact preferences that
- they prefer English or Spanish, we will send materials in their preferred language. As is
- standard, materials will be sent in English only at the VA. All materials will be sent on
- letterhead and branding appropriate and specific to each HCS. The letter will be signed by
- either the primary care provider for the patient or the site principal investigator.

- 173 Should an opt-out packet be returned by the United States Postal Services (USPS) due to an
- incorrect address, etc., a member of the study team will call the potential participant no more
- than two times to verify their address; should they not hear from the participant the patient will
- not be included in the study. Upon the deadline for response to the opt-out consent has
- expired, patients that have not opted-out will be randomized accordingly. Signed and returned
- opt-out forms will be securely stored in a locked filing cabinet (returned opt-out forms for VA
- patients will be securely stored at the VA).

Patient Identification Process

- From this pool of candidates, patients will be followed forward and those identified to have a gap
- of at least 7 days in one of the CV medications at any time during the two-year monitoring
- period will be randomized to one of the four study arms. For patients who are prescribed
- multiple CV medications, eligibility for randomization will be triggered by the first 7-day gap for
- any medication.
- 187 We have already developed algorithms that queries pharmacy data for a defined medication
- refill gap based on the date that the medication was supplied and the number of medication
- days supplied. This algorithm is in use for a medication adherence study currently. We will apply
- this algorithm across the 3 HCS to identify non-adherent patients.
- 191 Pharmacy data from UCHealth and Denver Health will be accessed through both hospital-
- specific pharmacy data and Surescripts, a network with existing relationships with both HCS
- that provides pharmacy refill data from over 95% of US pharmacies. Daily pharmacy data via
- 194 Surescripts is currently available at Denver Health, and is projected to become available at
- 195 UCHealth in the fall of 2019.
- Every 3 months for up to two years, we will assess whether there are new patients who have

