3.1 Analysis of primary composite PDC outcome

3.1.a Summary of modeling approach

We propose to calculate a composite PDC ratio of days covered for each subject and analyze it using a standard longitudinal model for monthly PDC values, with a linear mean model, and with robust standard error estimation and associated inference based on weighted Generalized Estimating Equations (GEE), e.g. Robins et al., 1995; Preisser et al., 2002. In more detail and with rationale:

Outcome distribution: Since data are in the form of a discrete proportion, our original proposal was based on Bernoulli/binomial models. However, treatment-blinded examination of a sample of outcome data showed that the binomial assumption will not apply due to spikes caused by common prescription lengths (e.g. 30 and 90 days), and strong overdispersion or equivalently lack of independence of daily outcome data over time. We considered alternative approaches such as Poisson with offset for number of observation days but similar challenges of spikes, overdispersion and lack of independence remain. Ultimately, with the large number of subjects available for analysis (~10,000) and the bounded distribution of PDC (between 0 and 1), central limit theorem arguments make standard linear modeling valid in this situation (e.g. Lumley et al., 2002), and robust inference methods described below provide additional assurance of valid inference even with heteroscedastic variance in the outcomes.

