Longitudinal models and GEE: To account for the situations of shortened PDC observation and possible resulting biases we will use a longitudinal model with PDC calculated for monthly intervals. We will use GEE with identity link and independence with unequal variances for the covariance structure. This approach provides robust and likely conservative (Hernán et al., 2002) estimation using empirical (sandwich) variance estimates, but is valid only for MCAR data. However, use of weighting can extend GEE to data missing at random (MAR). In this approach, observation-specific weights are equal to the inverse probability that the longitudinal value was observed. Probability of observation will be estimated by a logistic regression model for whether the value was observed (y/n), with covariates listed in section 3.1.c below. Weights greater than the 95th percentile of weights will be set to the 95th percentile weight. These methods can be implemented for example in SAS PROC GEE (Lin & Rodriguez, 2015) or R package wgeesel (Xu et al., 2018). We will use multiple imputation to impute missing covariate data. We will carry out the recommended sensitivity analyses to the MAR assumption using methods based on pattern mixture models and imputation, by assuming a range of

perturbations of imputed values and assessing differences in model conclusions (e.g. White et al., 2011; Fiero et al., 2017).

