Medications to include in composite PDC: We have considered three ways of selecting medications to include in the primary PDC outcome: PDC1) all medications on which a patient gapped at baseline, PDC2) all medications a patient ever gaps on, calculating PDC from the time of gap, and PDC3) all medications a patient was prescribed at baseline. Medications prescribed after the baseline gap and enrollment will not be included in any of these definitions of PDC, though they will be considered in secondary analyses. Each definition (1-3) has benefits and shortcomings. PDC1 is closest to a pure effect of the intervention, but exploratory analyses of pilot data have shown that many patients who gap in a medication and are randomized also gap in another medication shortly thereafter. Specifically, preliminary data indicate that ~16% of patients gap on an additional medication within 30 days of baseline and ~37% within 90 days. PDC1 will omit these other medications prescribed but not gapped on at baseline. PDC2 provides a similar estimate incorporating these later-gapped medications but excludes medications the patient may never gap on due to reminders for other medications. PDC3 provides an estimate of the overall effect of the interventions on medication patterns, incorporating indirect effects of reminders, but risks inflating PDC and diluting intervention effects by including medications the patient never gaps on. Our primary analyses will use PDC1, while PDC2 and PDC3 will be considered in secondary analyses.

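### The primary PDC model and its observation weights contain no term describing the baseline-gapped medications from which the outcome is built

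*Combined protocol and SAP*

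**What the plan says.** SAP section 3.1.c states that "The linear weighted GEE model for PDC and the logistic model for propensity of observation will each contain terms for" a single list of covariates. The list starts with health care system, then "number of CV medications prescribed at baseline (1-2 or 3+), calendar month of randomization", then arm, follow-up month and their interaction, then demographics, and ends with "comorbidity variables hypertension, hyperlipidemia, coronary artery disease, diabetes, atrial fibrillation, chronic heart failure" and further conditions. The one term about medication is a two-level count of CV drugs prescribed.

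The primary outcome is defined in section 3.1.b as "PDC1) all medications on which a patient gapped at baseline", out of 13 classes. Drugs prescribed but not in gap at baseline are left out. Section 3.1.a says "we will use a longitudinal model with PDC calculated for monthly intervals", with weights from the observation model.

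Section 3.1.a also reports what the treatment-blinded look at the outcome showed: "spikes caused by common prescription lengths (e.g. 30 and 90 days), and strong overdispersion". The SAP's response is to replace the binomial model by a linear mean model with robust inference. It adds no covariate for prescription length.

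The information is at hand. The protocol (Patient Identification Process) describes an algorithm that finds a "refill gap based on the date that the medication was supplied and the number of medication" days supplied.

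**The concern.** The outcome describes particular drugs, but the covariates describe the patient. A patient in the 3+ stratum may have one drug in gap or several, and the list cannot tell these apart. The SAP itself notes that many patients gap on a further drug soon after baseline (about 16% within 30 days), so number prescribed and number gapped are different quantities.

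Two things are at stake.

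- **Precision.** Baseline features of the gapped drugs may predict coverage. If so, leaving them out gives up precision that is almost free.
- **Weights.** Section 3.1.a says that truncation for reasons other than the two system disruptions is likely not completely at random. Provider termination is one of those reasons. The weighted analysis then relies on missingness at random given the 3.1.c list. Termination happens to a drug, and the list contains nothing about the drug.

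**Working it through.** **1. The plan's own figure.** Section 3.1.f uses a difference of 0.10, SD 0.22, two-sided level 0.05/6 and 80% power. A two-sample t-test gives 118.97, so 119 per arm. The stated figure is reproduced.

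**2. Precision at the achieved size.** Section 3.1.f gives 1,235 + 7,266 + 1,000 = 9,501 patients. With equal allocation that is 9,501/4, about 2,375 per arm. Stage 1 tests use level 0.05/3, so z = 2.394; 80% power adds 0.842.

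SE = SD × √(1 − R²) × √(2/n); detectable difference = (2.394 + 0.842) × SE.

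With R² = 0: SE = 0.22 × √(2/2,375) = 0.00638, and the detectable difference is 3.236 × 0.00638 = 0.0207. The R² added by the three terms is not in the documents, so a range is assumed:

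| Added R² (assumed) | Detectable difference, SD 0.22 | Power for 2 points, SD 0.22 | Detectable difference, SD 0.247 (protocol) | Power for 2 points, SD 0.247 |
|---|---|---|---|---|
| 0 | 2.07 points | 77.0% | 2.32 points | 65.4% |
| 0.05 | 2.01 points | 79.4% | 2.26 points | 68.0% |
| 0.10 | 1.96 points | 81.8% | 2.20 points | 70.8% |

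Power for the planned 10 points is about 100% in every row.

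As a rough anchor for the range, suppose half the patients have 90-day fills and their mean PDC differs by d. Then R² = d² × 0.25/0.22², which is 1.3% for d = 0.05, 5.2% for 0.10 and 11.6% for 0.15. Both the share and d are assumptions. The formula also ignores overlap with covariates already listed, so it overstates the added R².

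**3. Number gapped and the observation model.** Section 3.1.b sums covered days and observed days over the gapped drugs, with at-risk days counted per drug. If a patient's only gapped drug is stopped, the denominator for later months is zero and no outcome exists. If one of two is stopped, an outcome remains. With an assumed chance q that a drug is stopped by month 12, independent between drugs, the chance of no outcome is q for one drug and q² for two: 10% against 1% for q = 0.10, and 20% against 4% for q = 0.20.

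**4. Possible effect on the contrast.** Take days' supply as the omitted variable, with half the patients in each group, 20% of 30-day and 10% of 90-day patients truncated by month 12, and d = 0.10 (all assumed). The shift in an arm's month-12 mean is

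0.10 × [0.45/(0.45 + 0.40) − 0.5] = 0.0029, or 0.29 points.

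For d = 0.05 to 0.15 it is 0.15 to 0.44 points. If every arm has the same truncation pattern, it cancels in the contrast. If the 30-day group in one arm is truncated at 15% or 10% instead of 20%, the month-12 contrast is off by 0.08 to 0.44 points. The primary contrast combines all 12 months, so this is a figure for the last month only.

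**The case against.** The case for leaving the list alone is fair, and much of it stands.

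- Arms are randomized, so omitting a prognostic baseline variable does not confound the comparison, and sandwich errors remain valid. This stands in full.
- The trial enrolled 9,501 patients against a stated need of 476, so a small precision gain decides little. This stands for the planned effect. It is less comfortable for effects near 2 points, and the protocol itself notes that many earlier adherence interventions had very small effects.
- A reader might infer from the reported spikes that mean PDC differs between 30- and 90-day fills. The documents do not say so. They describe the shape of the distribution, as a reason to leave the binomial model, and the SAP answered that problem. The spikes also reflect fills during follow-up, not the last fill before the gap.
- A reader might also note that one fill covers 90/365 of a year against 30/365. This says nothing about annual PDC, because patients with shorter fills have more refill occasions.
- Class is partly represented: all five conditions that Table 1 of the protocol maps to drug classes are in the list, and section 3.1.d analyses each medication separately. This stands for class, but not for number gapped or days' supply.
- Departures from missingness at random are covered by pattern-mixture analyses, and unrecorded cancellations by a separate sensitivity analysis. These help, but they do not replace a known baseline predictor in the weight model.
- Completeness of days' supply in the three systems is not documented. However, a gap cannot be flagged without a supply date and days supplied, so values should exist for patients who were randomized.

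**Conclusion.** The omission is real and minor. No term in either model describes the drugs that make up the primary outcome. The treatment contrast is not confounded and inference is valid.

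The precision gain is unknown. It is worth about 0.11 points of detectable difference (2.07 to 1.96) if the added R² is as large as 0.10, taking SD 0.22 and no loss from 9,501 patients.

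The better reason to act is the weight model. Number gapped determines by construction whether an outcome survives a termination, and the SAP already doubts that such truncation is completely at random. The documents do not show that truncation differs between arms or depends on class or days' supply. It would therefore go too far to call the primary result biased; the point is that the missing-at-random assumption could be made more credible with data already collected.

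**What to change.** Before unblinding, add three terms to both models in section 3.1.c, using values fixed at or before randomization only, since later days' supply could respond to treatment:

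- number of medications in gap at randomization;
- class group of the gapped medication(s), for example indicators for the five groups in the protocol's Quantitative Analysis section;
- days' supply of the last fill before the gap, in categories that separate common fill lengths, with a stated rule when several drugs gapped.

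Set the categories in advance, and handle missing values by the multiple imputation already planned for covariates. If the sponsor prefers to keep the current list, it should give the reason and pre-specify a sensitivity analysis that includes these terms.

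The cost is a short revision of 3.1.c and a few extra parameters in a data set of about 9,500 patients. The drawback is a further change to a list already revised once after a blinded look at outcome data, so the revision should be dated and its reason recorded.
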